3.3.3 Investigator Training and Qualification

The investigator(s) will be trained before participation in the study during a site initiation by means of a detailed description of all study procedures including the methods of obtaining study endpoints (measurements). The examiner will be calibrated so that the difference is 1 mm or less between his or her measurements and the principal investigator. Each examiner will measure the recession depth on two subjects three times each during each calibration session. These measurements will be recorded on a case report form and analyzed to ensure each examiner's accuracy is 1 mm or less. Examiner recalibration will be performed at the six month follow-up visit to ensure that his or her accuracy in measuring recession depth remains within that limit. Any examiner who has greater than 1.0 mm variability

from the principal investigator will undergo retraining by the principal investigator, as necessary.

One examiner will make all the measurements for each subject. The investigator guarantees that the examiner, who has working experience with the probe, is well qualified.

All investigators will be noted on the Investigator's Agreement and appropriate qualifications (CV and license) will be maintained in the investigator file.

3.3.4 Blinding and Probe Calibration

All study staff, with the exception of the treating clinician will be blinded to the treatment administered. Only calibrated UNC 15 probes will be used.

3.4 Study Procedures

3.4.1 Pre-Operative Treatment

Medical examination and past history as well as dental examination and past history will be completed at this stage.

Within 32 days prior to surgery, the subject will undergo plaque removal and the test sites will be undergo to root planing and scaling (if determined to be appropriate treatment by the investigator). Two to four (2-4) weeks prior to the first study treatment, subjects may undergo plaque removal and root planing and scaling to the areas to be treated, if

appropriate. Also, they will receive personalized oral hygiene instructions to reach full-mouth plaque score (FMPS) <20% and full-mouth bleeding score (FMBS) <20%, which will be considered requirement for surgery to occur.

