	Assigning Relationship of Adverse Events to Treatment.....	48
	Serious Adverse Events	49
	Definition of a Serious Adverse Event.....	49
	SAE report to Sponsor and IRB	50
5.0	STATISTICAL AND ANALYTICAL PLAN	51
	Intent to Treat Population	51
	Safety Population	51
	Evaluable Population	51
	Missing Data	52
	Assessment of Safety	53
6.0	REGULATORY AND ADMINISTRATIVE REQUIREMENTS.....	53
6.1	IRB Requirements.....	53
6.2	Protocol Amendments	54
6.3	Informed Consent.....	55
APPENDIX I:	QUESTIONNAIRES/SURVEYS	56

PROTOCOL SYNOPSIS

Protocol Number	1015456
Title	A STUDY TO DETERMINE EFFICACY OF EASY GRAFT CLASSIC FOR THE TREATMENT OF PERI-IMPLANTITIS
Subject Population	Subjects with history of Moderate to Severe Peri-implantitis
Objectives	TO ASSESS THE EFFECTIVENESS OF EFFICACY OF EASY GRAFT CLASSIC
Number of Subjects	Maximum of 15 subjects
Number of Sites	Maximum 20 implants
Safety Endpoints	Assessments of subject safety will be based upon tabulations of the incidence of adverse events.
Efficacy Endpoints	
Stability and health of the attachment apparatus at 6 and 12 months by measuring:
 
 • Change from baseline in probing depth • Change from baseline in clinical attachment level • Change from baseline in width of the keratinized tissue • Change from baseline in radiographic A) bone regeneration ; B) pathology • Esthetic satisfaction from baseline to 12 months, as assessed by both the examiner and the subject using the Visual Analog Scale (VAS), prior to and after viewing baseline photos • Subject pain/discomfort questionnaire

CONFIDENTIAL AND PROPRIETARY INFORMATION OF Creighton University School of Dentistry Department of Periodontics

Protocol Number: CUSD2

Revision: October 22nd 2018

Original Issue Date: January 6th 2017

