3.0 STUDY DESIGN

3.1 Overall Study Design

This study will be case series, with two periodontists and an examiner. Both of the periodontists will perform surgical procedures and record surgical measurements. The blinded examiner will perform all other clinical assessments. 15 subjects will be enrolled. Written informed consent will be obtained from each subject prior to any study related procedures.

The study will follow subjects for safety and efficacy for 6 and 12 months after their surgical treatment.

Screening will take place no more than 32 days prior to the first treatment and will include the clinical assessments required to confirm eligibility. Clinical photograph, radiographs of the implant treated, clinical measurements will be taken and recorded (Pocked Depth, Mucosal Recession, Clinical Attachment Level). Two to four (2-4) weeks prior to the first study treatment, subjects may undergo plaque removal and root planing and scaling to the areas to be treated, if appropriate. Also, they will receive personalized oral hygiene instructions to reach full-mouth plaque score (FMPS) <20% and full-mouth bleeding score (FMBS) <20%, which will be considered requirement for surgery to occur.

The day of surgery will be designated as Day 0. Subjects will have peri-implant regeneration surgery.

If possible, implant crown will be removed with attention not to damage it. Healing screw will be placed on the implants. Upon flap elevation and debridement of the peri implant lesion, the operator will record the type of bony defect associated to the treated implant (see Inclusion criteria 3). Titanium Implant surface will be debrided with rotating burs and brushes (PERI-SET Swden&Martina Inc.), and decontaminated with EDTA gel (Straumann® PrefGel. pH neutral, 24% EDTA) for 2 minutes and with the alternation of Perio-Flow Chlorhexidine mouthwash (GUM® ParoEx®, Chlorhexidine Gluconate Oral Rinse USP 0,12%, SUNSTAR) saline water and H₂O₂ using cotton pellets. After the completion of these procedures, Easy-graft® CLASSIC will be placed to fill the peri-implant defect.

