3.2.1 Primary Efficacy Endpoints

- Change from baseline in probing depth
- Change from baseline in clinical attachment level
- Change from baseline in width of the keratinized tissue
- Change from baseline in radiographic a) bone gain; b) pathology
- Esthetic satisfaction from baseline to six months of all treated areas, as assessed by both the examiner and the subject using the Visual Analog Scale (VAS), prior to and after viewing baseline photos

- Subject pain/discomfort questionnaire

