3.3 Subject Eligibility

3.3.1 Inclusion Criteria

Subjects must meet the following inclusion criteria to be eligible for the study:

1. Subject has read and signed the IRB approved consent form before treatment.
2. Subject must be age 21 or above.
3. Subject must be willing and able to follow study procedures and instructions.
4. Subject affected by moderate to severe peri-implant disease*.
5. Treated chronic periodontitis and proper periodontal maintenance care,

Dental implant must meet the following criteria to be selected for the study:

1. Implant presenting PD \geq 6 mm
2. Radiographic implant bone loss more than 25% of the implant length (Apex of the implant to implant platform)²³.
3. Peri implant bone defect being a buccal dehiscence and semicircular bone resorption to the middle of the implant body, buccal dehiscence and circular bone resorption with lingual bone plate intact or circular bone resorption with buccal and lingual bone plates intact

²³ Froum SJ, Rosen PS. A proposed classification for peri-implantitis. *Int J Periodontics Restorative Dent.* 2012 Oct;32(5):533-40.

CONFIDENTIAL AND PROPRIETARY INFORMATION OF Creighton University School of Dentistry Department of Periodontics

Protocol Number: CUSD2

Revision: October 22nd 2018

Original Issue Date: January 6th 2017

4. Single tooth implant restoration or implant supported fixed partial denture.

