3.4.2 Study Treatments

Screening will take place no more than 32 days prior to the first treatment and will include the clinical assessments required to confirm eligibility. Informed Consent Form will be signed at Screening Visit (Visit 1). Clinical photograph, radiographs of the implant treated, clinical measurements will be taken and recorded (Pocked Depth, Mucosal Recession, Clinical Attachment Level).

The day of surgery will be designated as Day 0. Subjects will have peri-implant regeneration surgery.

Whenever possible implant crown will be removed and cleaned. Healing screw will be placed on the implant. Upon flap elevation and debridement of the peri implant lesion, the operator will record the type of bony defect associated to the treated implant (see Inclusion criteria 3). Titanium Implant surface will be debrided with rotating burs and brushes (PERI-SET, Sweden&Martina Inc.), and decontaminated with EDTA (PrefGel: Straumann) for 2 minutes and with the alternation of Perio-Flow Chlorhexidine mouthwash (GUM® ParoEx®, Chlorhexidine Gluconate Oral Rinse USP 0,12% SUNSTAR), saline water and H₂O₂ using cotton pellets. After the completion of these procedures, Easy-graft® CLASSIC will be placed on the peri-implant defect surface. GUIDOR® Bio-resorbable Matrix Membrane will be

placed on top of the easy-graft classic and stabilized. If the implant crown was successfully removed, flaps will be primary closed and the implant will be covered completely. Second stage, minimally invasive surgery to gain access to the implant will be performed at 6 months. Intraoperative and postoperative measurements will be made and the flap will be closed with sutures. Patients will be instructed to take 500 mg of amoxicillin three times a day for 7 days, starting at least one hour prior the procedure.

Fifteen (15) male or female subjects, aged 21 to 85 years, will be recruited for the study from existing patient databases, as well as, from screenings of volunteers responding to advertisements, if necessary.

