3.6.2 Baseline/Treatment (Visit 2)

Visit 2 may occur concurrently with Visit 1. If separate visits are to occur, Visit 2 must occur within 32 days of the screening examine.

- Examiner calibration (for first 2 subjects enrolled only)
- Preoperative and Intraoperative digital photographs
- Concomitant medications
- Surgical procedure
- Post-operative instructions
- Collection of any Adverse Events

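### The only scheduled pre-operative PD and CAL readings are the screening readings, taken before the preparatory hygiene phase and partly used for eligibility, so change from baseline can include pre-surgical improvement

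*Combined protocol and SAP*

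**What the plan says.** Section 3.1 of the protocol describes an uncontrolled design: "This study will be case series, with two periodontists and an examiner". The synopsis sets "Maximum of 15 subjects" and at most 20 implants. Section 3.2.1 lists among the primary endpoints "Change from baseline in probing depth" and "Change from baseline in clinical attachment level". An implant qualifies under section 3.3.1 by "Implant presenting PD \geq 6 mm", among other criteria.

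Section 3.4.2 places the pre-operative readings at screening: "Clinical photograph, radiographs of the implant treated, clinical measurements will be taken and recorded (Pocked Depth, Mucosal Recession, Clinical Attachment Level". Section 3.6.1 (Visit 1) lists PD and CAL among the eligibility assessments, followed by cleaning, hygiene instruction and plaque control.

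Section 3.4.1 then describes the preparation: "Within 32 days prior to surgery, the subject will undergo plaque removal and the test sites will be undergo to root planing and scaling". That sentence goes on to make the scaling conditional on the investigator's judgement. The next one places optional plaque removal and scaling two to four weeks before surgery. Surgery requires full-mouth plaque and bleeding scores below 20%, whereas section 3.3.2 excludes only subjects with a plaque index above 50%.

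The only pre-operative record in the Visit 2 list (section 3.6.2), other than concomitant medication and a calibration exercise for the first two subjects, is "Preoperative and Intraoperative digital photographs". The list has no PD or CAL. Section 3.6.2 also allows Visits 1 and 2 to be the same visit. Section 5.0 does not define baseline.

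**The concern.** A change score measures what happened between its two readings. Here the first reading comes before a phase intended to reduce plaque and inflammation, and the second comes months after surgery. Any shallowing of pockets during preparation is then reported as change after surgery.

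The screening PD also decides entry. Implants whose reading happened to be high are more likely to be enrolled, and a repeat reading would on average be lower with no treatment at all. Both effects make PD change look more favourable. With no control arm and no second pre-operative reading, no later analysis can separate them from the surgical result, and the missing reading cannot be recovered once the operation is done.

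Baseline also differs in meaning between subjects: some will be scaled after it, some will not, and some may be read on the day of surgery.

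**Working it through.** The plan states no effect size, SD or sample-size derivation, so there is no figure of its own to reproduce. The check has two parts.

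**1. Tracing PD and CAL to the day of surgery**

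| Place | PD and CAL before surgery |
|---|---|
| 3.1 and 3.4.2 | recorded at screening |
| 3.6.1, Visit 1 | listed, as eligibility assessments |
| 3.4.1, preparation | none |
| 3.6.2, Visit 2 | none |
| Flowchart | marked at Visit 1, then not until Visits 6 and 7 |
| 3.7, defect examination at surgery | bone measurements only |

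Section 3.1 puts consent before any study procedure, and section 3.4.2 has it signed at Visit 1. Study scaling therefore cannot come before Visit 1. The number of scheduled PD or CAL readings after preparation and before incision is zero. The Visit 1 value is the baseline by elimination, although sections 3.2.3 and 3.6.2 attach that word to Visit 2.

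Write S for the screening reading, D for a Day 0 reading and F for follow-up. The reported change is S − F = (S − D) + (D − F). The plan never observes D, so S − D stays inside the result.

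**2. Size of S − D**

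*Preparatory effect.* The documents give no value. For scale only, 0.5/2.78 = 18%, where 2.78 mm is the meta-analytic PD reduction cited in sections 1.0 and 2.0.

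*Regression to the mean, single site.* Expected fall = (1 − ρ) × SD × φ(a)/(1 − Φ(a)), with a = (6 − μ)/SD. SD² = 1.2² + e², and ρ = 1.2²/SD². Assumptions, not from the documents: true SD 1.2 mm, mean μ of 5 to 6 mm, reading-error SD e of 0.5 to 1.0 mm.

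- μ = 6, e = 0.5: SD = 1.30, 1 − ρ = 0.148, a = 0, ratio 0.798. Fall = 0.148 × 1.30 × 0.798 = 0.15 mm.
- μ = 5, e = 1.0: SD = 1.56, 1 − ρ = 0.410, a = 0.64, ratio 1.245. Fall = 0.410 × 1.56 × 1.245 = 0.80 mm.
- With μ = 7 the range drops to 0.07 to 0.28 mm.

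A different set of assumptions (mean 5 to 7 mm, total SD 1.5 to 2.0 mm, test-retest correlation 0.7 to 0.9) gives 0.06 to 0.68 mm.

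*Six sites.* Section 3.5.3 reads PD at six locations, and the plan does not say how they become one value per implant. I simulated this with the same SDs, means of 5 to 6 mm and an assumed within-implant correlation of true depth of 0.3 to 0.8. An implant entered if any site read at least 6 mm.

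| Summary used for change | Fall from regression alone |
|---|---|
| Same deepest site followed | 0.30 to 1.30 mm |
| Deepest reading at each visit | about 0.02 to 0.21 mm |
| Mean of six sites | 0.01 to 0.08 mm |

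The selection effect therefore depends mainly on a summary that the plan leaves open. CAL is not the selection variable, so it is affected only through its correlation with PD and was not simulated.

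**The case against.** The strongest reply is that the bias may be small. Entry requires treated periodontitis with maintenance care, which could limit any further gain from cleaning. Scaling is discretionary, and a subject operated on at the screening visit has little or no preparatory phase. The criteria on disease severity, bone loss above 25% of implant length and defect shape favour truly deep pockets, which weakens regression to the mean. If the six-site mean is analysed, regression is negligible. All of this stands, and it limits what can be said about size. It does not supply the missing reading, and any preparatory effect remains under every summary.

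It can also be said that this is a small case series with no hypothesis test or threshold, and that the lack of a comparator is the larger attribution problem. That is fair and lowers the severity. PD and CAL changes are still listed as primary, and their reference value is cheap to obtain.

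A reader might infer that a fixed share of this trial's PD result, such as the 18% above, is spurious. The documents do not support that: the preparatory effect is unmeasured, and 2.78 mm is literature context, not a target. Nor do they support the inference that every subject is affected.

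**Conclusion.** The concern holds in a limited form. The only scheduled pre-operative PD and CAL values come before the preparatory phase. Where Visits 1 and 2 are separate, any improvement in that phase is counted as post-surgical change. Selection on PD may add regression to the mean in PD, and indirectly in CAL.

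The total size cannot be derived from the documents. Under the stated assumptions the selection part ranges from under 0.1 mm (six-site mean) to 1.3 mm (same deepest site followed). The preparatory part is unknown.

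A reader might also infer that a Day 0 reading removes both effects and isolates the graft. It does neither completely. Late effects of preparation and slow true fluctuation remain, and regression returns if sites or implants are chosen again on the Day 0 reading. Graft, membrane, debridement, decontamination and antibiotic stay inseparable without a comparator. The plan should be corrected, but the gap does not by itself invalidate the series.

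**What to change.** - Keep the Visit 1 readings for eligibility and for choosing any index site.
- Add PD with bleeding on probing, recession and CAL to the Visit 2 list (3.6.2) and the flowchart, read by the same examiner before anesthesia and incision.
- In section 5.0, define these Day 0 values as baseline for all PD, recession and CAL changes.
- Fix the per-implant summary in advance, for example the six-site mean or the index site chosen at Visit 1. Do not select implants or sites again on the Day 0 reading.
- Report the Visit 1 to Day 0 change separately.
- Reconcile the sentence allowing concurrent Visits 1 and 2 (3.6.2) with the two-to-four-week preparation (3.4.1), and report how many subjects had concurrent visits.

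The cost is a few minutes of probing at a visit that already takes place, plus a short amendment. The reported changes may be somewhat smaller. For subjects already operated on, state that baseline is the screening value and show them separately.

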3.4.2 Study Treatments

Screening will take place no more than 32 days prior to the first treatment and will include the clinical assessments required to confirm eligibility. Informed Consent Form will be signed at Screening Visit (Visit 1). Clinical photograph, radiographs of the implant treated, clinical measurements will be taken and recorded (Pocked Depth, Mucosal Recession, Clinical Attachment Level).

The day of surgery will be designated as Day 0. Subjects will have peri-implant regeneration surgery.

Whenever possible implant crown will be removed and cleaned. Healing screw will be placed on the implant. Upon flap elevation and debridement of the peri implant lesion, the operator will record the type of bony defect associated to the treated implant (see Inclusion criteria 3). Titanium Implant surface will be debrided with rotating burs and brushes (PERI-SET, Sweden&Martina Inc.), and decontaminated with EDTA (PrefGel: Straumann) for 2 minutes and with the alternation of Perio-Flow Chlorhexidine mouthwash (GUM® ParoEx®, Chlorhexidine Gluconate Oral Rinse USP 0,12% SUNSTAR), saline water and H₂O₂ using cotton pellets. After the completion of these procedures, Easy-graft® CLASSIC will be placed on the peri-implant defect surface. GUIDOR® Bio-resorbable Matrix Membrane will be

placed on top of the easy-graft classic and stabilized. If the implant crown was successfully removed, flaps will be primary closed and the implant will be covered completely. Second stage, minimally invasive surgery to gain access to the implant will be performed at 6 months. Intraoperative and postoperative measurements will be made and the flap will be closed with sutures. Patients will be instructed to take 500 mg of amoxicillin three times a day for 7 days, starting at least one hour prior the procedure.

Fifteen (15) male or female subjects, aged 21 to 85 years, will be recruited for the study from existing patient databases, as well as, from screenings of volunteers responding to advertisements, if necessary.

